Engaging Working Memory and Distress Tolerance to Aid Smoking Cessation
NCT03565497
R21 DA046963

Updated: 8/5/2019

PROTOCOL

Design Overview

This study is designed to evaluate the success of mechanistic target engagement in two specific contexts: under standard smoking conditions and under nicotine deprivation (stress) conditions. After screening, consent, and baseline assessment, participants selected on the basis of inclusion/exclusion criteria will be randomized to one of three intervention conditions: (1) a health-education control condition (CC), (2) a mindfulness training condition (MT), or (3) a mindfulness training condition combined with training applying mindfulness skills in the context of interoceptive exposure (Mindfulness+IE). Following 6 sessions of these interventions, delivered over 3 weeks, participants will then undergo the standard smoking assessment of mechanistic targets. Two days later (and matching the progression to quit-attempt challenges following treatment), participants will undergo the deprivation window assessment (14 hours of smoking abstinence) of these same mechanistic targets, followed by evaluation of lapse behavior and smoking topography in the McKee paradigm to yield: (1) latency to initiate smoking during a monetarily reinforced delay period, (2) the number of cigarettes smoked during a subsequent 60-minute self-administration period, and (3) exploratory analysis of smoking topography: puff volume, puff duration, and inter-puff interval. Participants will be recruited to Boston University through study advertisements targeted to low SES neighborhoods, with attention to health service centers and religious institutions serving low SES individuals. Investigators will work closely together to ensure the scientific integrity (rigor and reproducibility) of the project and data analyses.

Participant Selection

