Following telephone screening for basic eligibility, participants will be scheduled for an informed consent interview and subsequent baseline assessment session. Interventions are to be completed over the subsequent 3 weeks, and post-treatment assessments of the mechanistic targets are scheduled for one-week (standard smoking assessment) and one week + 2 days (deprivation-window assessment) from the last intervention session. For the standard smoking window assessments, participants are asked to smoke .5 hour before the scheduled assessment session. The deprivation-window assessment is scheduled two days later, (for example, scheduled for 12:00 noon, with smoking to cease at 10PM the night before). Upon arrival to the lab, nicotine abstinence will be verified by expired CO levels, as determined by a cut-off of half of the participant's screening session CO concentration or <10 PPM (those failing will be rescheduled). After verification of abstinence, participants will complete assessment of the triple-risk mechanistic target variables. These assessments will be followed by the McKee Lapse protocol ([name], *Study Consultant*, will train the study team and help monitor quality in these procedures): participants will be instructed that over the next 50 min, they will have the option to initiate a cigarette self-administration (smoking) session at any point or to delay initiation in exchange for monetary reinforcement. If participants choose to delay, they will be awarded funds for each 5-minute increment they are able to resist smoking. Once participants choose to end the delay period in order to smoke (or resist smoking for the entire 50 minute delay period), they will then participate in a 60-minute cigarette self-administration session, in which they will be given the choice to either smoke their

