preferred brand of cigarettes or receive monetary reinforcement for cigarettes not smoked. Participants will be given funds at the beginning of the self-administration session and will lose a portion of the funds for each cigarette smoked. When participants smoke in this protocol, we will use the Clinical Research Support System (CReSS; Plowshare Technologies, Borgwaldt KC, Inc) to measure smoking topography. The reliability and acceptability of use of the portable CReSS device is well documented,^{88,94} and is recommended over direct observation. Topography data will include puff CO volume, puff duration, and inter-puff interval. Puff level data will be averaged to compute mean topography variables for each participant.

Baseline Assessments

- **Demographics.** Participants will be asked to provide standard demographic information (age, gender, race/ethnicity) as well as history of medical problems and current treatments.
- **Smoking History Questionnaire.** Smoking history and pattern will be assessed with a semi-structured interview with items targeting smoking frequency, age of smoking initiation, years of being a regular smoker, etc. The Timeline follow-back method will be used to establish degree of cigarette use in the last 30 days (a baseline predictor).
- **Fagerström Test for Cigarette Dependence (FTCD).** The FTCD is a six-item scale designed to assess gradations in cigarette dependence.⁹⁵ The FTCD will be used as a baseline covariate in the analyses.
- **Questionnaire of Smoking Urges-Brief (QSU-Brief).** The QSU-Brief measures urge to smoke and craving.^{96,97} The baseline and deprivation window Total Craving Scores will be used as predictors.
- **Executive Function – Behavioral Regulation.** Baseline levels of behavioral regulation will be assessed with the Behavioral Regulation Index from the from the SOBC assay, Behavioral Rating Inventory of Executive Function – Adults (BRIEF-A, <http://scienceofbehaviorchange.org/measures/>).
- **Psychological Distress.** Baseline levels of psychological distress will be assessed with the SOBC assay, Kessler Psychological Distress Scale (K6+, <http://scienceofbehaviorchange.org/measures/>).

Mechanistic Targets: The Triple-Risk Variables

Each of the mechanistic targets will be assessed at the post-intervention standard-smoking and deprivation-window assessments.

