Aim 2: For Aim 2, we will examine the bivariate associations between the triple risk variables and McLee Lapse outcomes. We will attempt to balance the need to determine which individual variables at which assessment context are related to which outcomes, with the need to minimize the number of tests. Thus, multivariate MRM (MMRM) will be used with the 2 McLee Lapse outcomes as the multiple DVs. One MMRM will be performed for each individual risk variable, with the IVs in each MMRM being the 2 assessments (smoking context and deprivation context) of the individual risk variable. This MMRM will be compared to the same MMRM that constrains the coefficients of each IV to be equal. If the likelihood ratio test indicates that the constrained model does not fit the data worse than the unconstrained model, then the relation between the risk factor and the outcomes does not differ by assessment context. If the test is significant, assessment context would be considered a moderator of the relation between the risk factor and outcome. Further, we will include a dummy variable to differentiate the 2 outcomes (0=latency, 1=number of offers of cigarettes resisted). If an interaction between that dummy variable and an IV regression coefficient is significant, the relation between the risk factor and outcome is different for the 2 outcomes.

Aim 3: To determine which of the individual risk assays are related to outcomes over and above the other factors, including consideration of the assessment context of each risk factor, we will perform analyses similar to the MMRM in Aim 2 with the following differences: 1) if Aim 2 shows that the relation between a risk assay and outcomes did not differ by context, the 2 measures of the risk factor will be averaged across the 2 contexts and used as a single predictor, and 2) all the risk factors will be entered as simultaneous predictors of outcomes. Non-significant predictors will be dropped and the analysis rerun.

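### The second lapse outcome is cigarettes smoked in the protocol but offers resisted in SAP Aim 2; entering the protocol's count unreversed would make the outcome-difference test misreport equal harm as a difference

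*SAP*

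**What the plan says.** The protocol's Design Overview lists two main results of the McKee paradigm: "1) latency to initiate smoking during a monetarily reinforced delay period" and "2) the number of cigarettes smoked during a subsequent 60-minute self-administration period". Smoking topography is exploratory.

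The protocol section on procedures and the McKee protocol describes how these arise. In the 50-minute delay period, participants who hold off are paid: "they will be awarded funds for each 5-minute increment they are able to resist smoking". In the 60-minute session that follows, they choose between smoking their "preferred brand of cigarettes or receive monetary reinforcement for cigarettes not smoked". They start that session with funds and "will lose a portion of the funds for each cigarette smoked".

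SAP Aim 2 puts the two lapse outcomes into one multivariate model per risk variable and states: "we will include a dummy variable to differentiate the 2 outcomes (0=latency, 1=number of offers of cigarettes resisted". A significant interaction between this dummy and a risk variable's coefficient is to be read as a relation that differs between the outcomes. Aim 3 uses a similar model with all risk factors entered together, drops non-significant predictors and reruns. Neither document links cigarettes smoked to offers resisted, and neither mentions reverse-scoring.

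**The concern.** The outcome that the protocol defines and the outcome that the SAP models have different names, and they run in opposite directions. Longer latency and more offers resisted are both favourable; more cigarettes smoked is unfavourable. An analyst who follows the protocol will hold a smoked count, and an analyst who follows the SAP needs a resisted score whose construction is not given.

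The direction matters because of the SAP's decision rule. The interaction test shows whether a risk variable acts differently on the two outcomes only if both are scored the same way. With the raw smoked count in the second slot, a variable that shortens latency and increases smoking to the same degree would be reported as acting differently on the two. Standardising removes the difference in units but not the difference in sign.

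**Working it through.** **Definitions side by side**

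| Item | Source | Direction |
|---|---|---|
| Latency to smoke | Protocol, Design Overview; SAP Aim 2 (dummy = 0) | higher = better |
| Cigarettes smoked in 60 minutes | Protocol, Design Overview | higher = worse |
| Offers of cigarettes resisted | SAP Aim 2 (dummy = 1) | higher = better |
| Scheduled or counted offers | Procedures section | none described |
| Number of cigarettes available | Procedures section | not stated |

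**The plan's nearest figure.** The SAP's power paragraph gives d = .39 for Aim 2 at N=75 with power above .80. The point does not rest on it, and it cannot be reproduced because alpha, variance components and correlations are not given. Assuming two-sided 5%:
- Converting d to a correlation gives r = .39/√(.39² + 4) = .191 and power Φ(atanh(.191)·√72 − 1.96) = .38.
- Reading .39 itself as a correlation gives power .94.

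The SAP's figure is therefore not called wrong. These two readings only help to set the range of slopes below.

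**Algebra.** Let b1 be the risk variable's slope on latency and b2 its slope on a resisted score, both standardised. Suppose smoked = K − resisted, with K the same for everyone. The slope on smoked is then −b2, and K goes into the intercept.
- Coded as resisted: interaction = b2 − b1; equally weighted shared slope = (b1 + b2)/2.
- Coded as smoked: interaction = −b2 − b1 = −2 × (shared slope under resisted); shared slope = (b1 − b2)/2 = −½ × (interaction under resisted).

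The two quantities exchange roles. Three cases follow:
- Equal harm, b1 = b2 = −.30. Resisted: interaction 0, shared slope −.30. Smoked: interaction .60, shared slope 0.
- Opposite effects, b1 = −b2. Coded as smoked, the interaction is zero and a true difference is missed.
- Effect on one outcome only. If b2 = 0 the interaction is −b1 under both codings. If b1 = 0 it changes sign but not size. The miscoding does not hide or create a difference here.

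**Simulation.** Inputs: N=75 (SAP power paragraph); 4,000 runs per cell; normal standardised outcomes; equal harm on both; two-sided 5%. The slopes, and the residual correlations between latency and the resisted score, are assumptions. The model has one risk variable, without the two contexts or the five covariates. The table gives the percentage of runs in which each test rejects.

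| Slope size | Residual correlation | Resisted: shared slope | Resisted: interaction | Smoked: shared slope | Smoked: interaction |
|---|---|---|---|---|---|
| .19 | .3 | 52.9 | 4.6 | 4.6 | 52.9 |
| .19 | .7 | 43.8 | 5.0 | 5.0 | 43.8 |
| .30 | .3 | 90.3 | 5.0 | 5.0 | 90.3 |
| .30 | .7 | 81.2 | 5.6 | 5.6 | 81.2 |
| .39 | .3 | 99.1 | 5.2 | 5.2 | 99.1 |
| .39 | .7 | 97.3 | 5.2 | 5.2 | 97.3 |

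The exchange is exact, as the algebra requires. The percentages are ordinary power values at the assumed inputs.

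**What does not change.** With the interaction in the model and latency coded 0, the risk variable's own coefficient is the latency slope, whichever way the second outcome is coded. In one simulated data set, the Aim 2 likelihood ratio test for assessment context was 4.43 under both codings with outcome-specific slopes. With one slope shared across outcomes it was 1.74 (resisted) and 2.10 (smoked).

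**The case against.** The strongest reply is that the SAP contains no sign error. It pairs latency with a resisted score, so both outcomes run the same way, and the harm needs an analyst to put a raw smoked count in a slot labelled as resisted. That stands. A reader might infer that the Aim 2 analysis as written reverses its meaning; the text does not support this.

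The second reply is that a resisted score has a natural source. Participants are paid for cigarettes not smoked, so a constant minus the number smoked is a plausible reading, and a constant common to everyone alters no linear slope or interaction. This also stands in part. It would be too strong to say that the score cannot be obtained from the data. It is not defined as documented: no offers are described, no number available is stated, and neither document makes the conversion.

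The third reply is that the SAP names no slope shared across outcomes. A reader might infer that Aim 3 will discard true predictors through cancellation. That would follow only if Aim 3 judged predictors on a shared slope, which the SAP does not say.

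Finally, Aim 1, on engagement of the mechanistic targets, does not use the lapse outcomes, and the SAP's opening note says the full plan could not be enacted validly because of limited sample size. Both limit the practical effect. The note does not say which analyses were dropped, and it does not settle which outcome is meant.

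**Conclusion.** The concern holds as an inconsistent and incompletely defined second lapse outcome, with a conditional consequence. The conflict is in current text, and both documents carry the same update date, so neither plainly supersedes the other.

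If the protocol's count is analysed unreversed under the SAP's rule, equal harm on both outcomes is reported as a difference in 44% to 99% of runs over the assumed range (slopes .19 to .39, residual correlations .3 to .7), against about 5% with aligned coding. These rates are conditional on that miscoding and on the assumed values; they say nothing about how likely the miscoding is. The exchange of the two tests is algebraic and does not depend on the assumed values. Outcome-specific slopes remain valid, apart from the sign with which the smoking slope must be read. Cancellation arises only for a slope shared across outcomes.

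**What to change.** In SAP Aims 2 and 3, replace offers of cigarettes resisted with the protocol's outcome, cigarettes smoked in the 60-minute session, so that both documents name the same variable.

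For the stacked model and its dummy-by-risk-variable test, standardise both outcomes, reverse the sign of the smoking score so that higher means better for both, and state this in the SAP. The common scale is needed because minutes and a count are otherwise not comparable.

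The SAP's opening paragraph allows other distributions and link functions, and a negated count cannot be fitted with a count model. If one is used, keep the raw count, fit outcome-specific slopes, and compare them only after allowing for the opposite direction and the different scale. State also whether Aim 3 judges predictors on outcome-specific or shared slopes.

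Report the raw count descriptively in either case. The cost is SAP wording and one recode; no new data are needed.

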Engaging Working Memory and Distress Tolerance to Aid Smoking Cessation

NCT03565497

R21 DA046963

Updated: 8/5/2019

Analytic Plan

Note: Due to limited sample size the full analytic plan for this project could not be enacted validly.

Analyses for outliers, non-normal distributions, nonlinear relations, and influence statistics will be conducted; data transformations will be considered where appropriate. We will analyze data using mixed effects regression models (MRM) because they allow inclusion of all participants regardless of missing data (which improves power and generalizability) and are the recommended method for longitudinal data analysis (Hamer & Simpson, 2009). For each analysis, the distribution of the DVs will be evaluated and appropriate linking functions and outcome distributions will be used if the DVs are not normally distributed (in these cases the analysis will be generalized linear mixed models). For all analyses, the following baseline assessments will be included as covariates in the analyses: cigarette use in the last 30 days, FTCD score, QSU score, BRIEF-A scores for the Behavioral Regulation Index, and psychological distress from the K6+ symptoms.

Aim 1. We will perform repeated-measures MANCOVAs using MRMs. IVs will be intervention condition (3 levels) and assessment context (smoking vs. deprivation; 2 levels). One MANCOVA will be performed for each of the three risk categories (stress reactivity, WMC, DT) with the multiple measures of each risk factor being the multivariate DVs. For Aim 1a, we will use contrasts to test whether Mindfulness and Mindfulness+IE will each significantly improve stress reactivity, WMC, and DT relative to the control condition (CC), during the standard smoking assessment. For Aim 1b, we hypothesize that Mindfulness+IE will significantly improve stress reactivity, WMC, and DT relative to both the Mindfulness and CC conditions, during the smoking deprivation assessment.

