Exploratory Analyses: 1) In consideration of sex as a biological variable, sex and the interactions between sex and all predictors will be considered in exploratory analyses for each Aim. 2) We will examine whether ASI moderates the effects of treatment condition and context (stress) on the risk categories in Aim 1, by adding ASI and its interaction with the treatment condition and context to the MMRMs in Aim 1. 3) We will examine smoking topography as a predictor of outcomes in Aims 2 and 3. 4) We will examine number of intervention sessions attended and dropouts to aid data interpretation and future study planning.

Power Analysis. We used PinT 2.12 (Power in Two-Level models) to calculate the smallest effect size detectable given our N=75 at the deprivation assessment. Since no power analysis programs are available for multivariate MRM, we performed power analyses for the univariate MRMs knowing that power for the multivariate MRMs will be greater.¹⁰⁸ PinT indicated that we had greater than .80 power to detect an effect size of $d = .40$ for **Aim 1**, $d = .39$ for **Aim 2**, and $d = .48$ for **Aim 3**. As per research detailed above,^{54,63,64,71,82,109} there is preliminary evidence indicating that our interventions have the ability to activate mechanistic targets, and for mechanistic targets to be related to clinical outcomes, at effect sizes beyond these powered values.

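### Aim 3's planned simultaneous model answers its question, but the SAP then prunes and refits without saying which model is reported; the Aim 2 and Aim 3 models also leave out randomised condition

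*SAP*

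**What the plan says.** SAP, Aim 3 states its purpose as: "To determine which of the individual risk assays are related to outcomes over and above the other factors". The model fits that purpose, because "all the risk factors will be entered as simultaneous predictors of outcomes". The closing sentence then reads: "Non-significant predictors will be dropped and the analysis rerun". The SAP gives no threshold for dropping. It does not say whether dropping is done once or repeatedly, or which of the two models supplies the reported coefficients.

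SAP, Aim 2 says "we will examine the bivariate associations between the triple risk variables and McLee Lapse outcomes". There is one model per risk variable, "with the IVs in each MMRM being the 2 assessments (smoking context and deprivation context) of the individual risk variable", plus a dummy that separates the two outcomes. Aim 3 is the Aim 2 model with two listed changes, and neither brings in randomised condition. The covariates set for all analyses are five baseline measures, and condition is not one of them. Condition is an independent variable in Aim 1. It appears again only in the exploratory ASI moderation, which works "by adding ASI and its interaction with the treatment condition and context to the MMRMs in Aim 1".

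Aim 2 also compares a model with equal coefficients for the two contexts against one with free coefficients. If the likelihood-ratio test is not significant, "then the relation between the risk factor and the outcomes does not differ by assessment context", and Aim 3 then averages the two scores.

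The note at the head of the SAP says that the sample proved too small for the whole plan to be carried out validly.

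**The concern.** A coefficient given all other assays and a coefficient given only the surviving assays are different quantities. Aim 3 asks for the first, and its last step produces the second. If the pruned fit is what gets reported, a retained assay takes credit for any correlated, truly contributing assay that missed p<.05. Its interval is also computed as if the set of predictors had been fixed in advance.

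Leaving out condition is a separate matter. Aim 1 expects the interventions to shift these same targets. If they also shift lapse by another route, pooling the three arms produces a target–lapse association even where none exists within any arm. Aims 2 and 3 carry the claim that the targets relate to lapse, so both points bear on how that claim may be read.

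**Working it through.** **Inputs.** Seven assays (Protocol, Mechanistic Targets): PANAS and WSWS; N-back, digit span and spatial span; ASI-3 and MTPT-C. Five covariates (SAP, Analytic Plan). N=75 and d=.48 for Aim 3 (SAP, Power Analysis). Assumptions, because the documents do not give them: two-sided .05, the correlations between assays, how many assays contribute, and the sizes of the arm shifts. The Protocol says only that self-report and behavioural distress tolerance correlate partially.

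**1. The plan's own figure.** The PinT result (power above .80 at d=.48) cannot be rebuilt, because its variance components and number of predictors are not given. Read as a correlation, r = .48/√(.48²+4) = .48/2.057 = .233, with power about .53 at N=75. Read as a standardised coefficient, power is about .997. The figure is neither confirmed nor refuted. Below, .23 serves only as an example of a modest standardised partial coefficient.

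**2. Algebra of dropping.** Take two assays with true coefficient b each and correlation ρ. If one is dropped, the other's expected coefficient becomes b(1+ρ). For b=.23 this is .23×1.3=.299 at ρ=.3 and .23×1.5=.345 at ρ=.5. At ρ=0 nothing moves.

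**3. Simulation of pruning.** Outcome variance 1, equal intercorrelation ρ, covariates independent of the assays, full fit, then one refit on the terms with p<.05. Coverage is of the coefficient adjusted for all seven assays, among retained real assays. Variance explained is m·b² + m(m−1)·b²·ρ for m contributing assays.

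| Contributing assays | Variance explained, ρ=0/.3/.5 | Pruned v full, ρ=0 | ρ=.3 | ρ=.5 |
|---|---|---|---|---|
| one at .40 | .16/.16/.16 | 96 v 97% | 96 v 97% | 94 v 97% |
| two at .40 | .32/.42/.48 | 96 v 97% | 95 v 97% | 91 v 97% |
| one at .23 | .05/.05/.05 | 94 v 95% | 92 v 94% | 87 v 91% |
| two at .23 | .11/.14/.16 | 94 v 95% | 85 v 93% | 69 v 91% |
| three at .23 | .16/.25/.32 | 94 v 95% | 81 v 94% | 58 v 93% |

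Repeat runs moved these by up to two or three points. Assays at .40 are retained about 73–96% of the time. Where two or three contribute at .23 and ρ is .3 or .5, each is retained only 31–46% of the time. Null assays are declared significant 3–4% of the time after pruning and 5% in the full model.

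A structure by category gives the same picture. With correlations of .5 within working memory and .1–.2 between categories, two contributing working-memory assays at .23 give 69–70% v 93%. Two in different categories give 87–89% v 93–94%.

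**4. Condition omitted.** Take 25 per arm, the same arm means on target and lapse, and no within-arm relation. For a single score, the spurious pooled slope is V/(1+V), where V is the variance of the three arm means. The false-positive column is simulated for the Aim 2 form (both context scores, 2-df test, between-context correlation .7).

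| Arm means (SD) | V | Slope | False positives without condition |
|---|---|---|---|
| 0/.4/.4 | .036 | .034 | 5–6% |
| 0/.4/.8 | .107 | .096 | 11% |
| 0/.8/.8 | .142 | .125 | 14–16% |
| 0/.5/1.0 | .167 | .143 | 19% |

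With condition included the rate is 5% throughout. In the full Aim 3 model the confounding persists when only some assays shift (6–7% at the smallest pattern and 12–29% at the largest, with one to three assays shifted). It nearly vanishes if all seven shift equally and correlate at .3–.5 (5–6%).

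**5. Context test.** If the two context coefficients are truly .3 and 0, power to detect the difference is 23–28%, 14–19% and 11–14% at between-context correlations of .5, .7 and .8. A non-significant result therefore says little about equality.

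**The case against.** The strongest reply is that the full model is already planned and decides which assays stay, so the question of which assays matter is answered before anything is dropped. Only coefficients and intervals suffer, and only if the refit is reported in place of the full fit. The large coverage losses also come from effects so modest that most real assays are missed anyway, and low power is then the larger problem. The simulation uses one normal outcome and seven predictors. The plan has two outcomes modelled jointly, a latency capped at 50 minutes, and 7 to 14 predictors. An unadjusted association is a legitimate target for an aim that calls itself bivariate. Near the effect that Aim 1 was powered for, d=.40, leaving out condition costs almost nothing.

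Much of this stands. The defect is an unspecified reported model, not a missing one. The percentages show direction and rough size, and are not predictions for this trial. The reassuring case has conditions of its own: two assays at .40 would explain 32–48% of outcome variance. Aim 3 is not bivariate, so the defence of Aim 2 does not carry over to it.

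A reader might infer more: that pruning manufactures false findings, that it distorts Aim 3 whatever the data, or that the pruned model is certain to be the one reported. The documents do not support this. Null false positives fall slightly. Inflation of retained .23 estimates is similar in the full model (1.4–1.8 times in both). The SAP is silent on which fit is reported.

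**Conclusion.** The point holds in limited form. Aim 3 leaves open which of two different sets of coefficients will be reported, and the pruned set does not answer its stated question. The harm ranges from negligible (strong effects, or nearly uncorrelated assays) to material (several modest, correlated contributors), and the documents do not show which case applies. Correlation within a category is plausible, since three of the assays measure working memory.

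Leaving condition out of Aims 2 and 3 is a real gap. Its effect is near nil at a 0.4 SD shift and becomes noticeable only if the arms move both target and lapse by clearly more than that. The SAP cites preliminary evidence of effects above its powered values, but no passage suggests shifts of .8–1.0 SD on both. A reader might take the omission to invalidate Aim 2, and that does not follow.

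Reading a non-significant context test as equality is a minor wording fault. Because of the SAP's opening note, all of this matters only for Aim 2 or Aim 3 results that are actually reported. For those, the change is worth making.

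**What to change.** - In Aim 3, name the full simultaneous model as the reported analysis. Give every assay's coefficient and 95% interval, significant or not. Label any reduced model as descriptive.
- Add two indicators for randomised condition to the Aim 2 and Aim 3 models. If the pooled bivariate association is wanted in Aim 2, show it beside the condition-adjusted one.
- In Aim 2, report the difference between the context coefficients with its interval, and describe any averaging in Aim 3 as a simplification that saves degrees of freedom.

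This needs SAP wording only and no new data. For retained assays the full-model intervals are 2–33% wider than the pruned ones. The upper end follows from the variance inflation with seven assays at ρ=.5: (1+5×.5)/[(1−.5)(1+6×.5)] = 3.5/2 = 1.75, and √1.75 = 1.32, plus a small loss of degrees of freedom. The condition indicators use two degrees of freedom and widen intervals by 1–2% if the arms have no effect. In the shifted-arm settings they change the width by −4% to +9%.

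### The SAP uses smoking topography to predict latency and the session count, although it is recorded after latency is fixed and is undefined for anyone who smokes nothing

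*SAP*

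**What the plan says.** The SAP, under Exploratory Analyses (item 3), says: "We will examine smoking topography as a predictor of outcomes in Aims 2 and 3". It gives no model for this analysis and no rule for participants without topography data.

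The outcomes are defined in the SAP under Aim 2, where "multivariate MRM (MMRM) will be used with the 2 McLee Lapse outcomes as the multiple DVs", coded "0=latency, 1=number of offers of cigarettes resisted". Aim 3 uses similar models. The protocol's Design Overview names the second outcome differently, as "the number of cigarettes smoked during a subsequent 60-minute self-administration period". It then lists a third product of the same paradigm: "exploratory analysis of smoking topography: puff volume, puff duration, and inter-puff interval".

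The order of events is in the protocol, under Procedures and the McKee Protocol:
- The delay period comes first. "Once participants choose to end the delay period in order to smoke (or resist smoking for the entire 50 minute delay period"), the 60-minute self-administration session begins.
- In that session participants may smoke their "preferred brand of cigarettes or receive monetary reinforcement for cigarettes not smoked", so smoking nothing is both possible and paid.
- "When participants smoke in this protocol, we will use the Clinical Research Support System" to capture topography. The puff-level readings are then averaged to one mean per participant.

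Topography appears neither under Baseline Assessments nor among the mechanistic targets, and no earlier topography measurement is described.

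**The concern.** A predictor should be measured before the outcome it predicts, and whether it is observed should not depend on that outcome. Topography fails the first condition for latency and both conditions for the session count.

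An association with latency could arise because a longer delay changes how people puff, with no influence in the other direction. An association with the count would be estimated only in people whose count is above zero. Reported as prediction of lapse, either result would suggest that puffing behaviour identifies who will lapse, which this design cannot show.

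**Working it through.** The documents give no figure for this analysis, so there is nothing to reproduce. The check is of time order and selection, followed by illustrations on stated assumptions.

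**Step 1: latency.** Latency is fixed when the participant chooses to smoke, or at 50 minutes. Topography begins with the first puff, which comes later. The order is reversed for every participant who has a topography value.

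Simulated illustration: topography has no effect on latency, but topography = 0.3 × latency + noise, with latency and noise each of unit variance. The expected correlation is 0.3/√(1 + 0.09) = 0.29. With N = 75 and 4,000 replicates, the mean correlation was about 0.28. It was significant at the 5% level in 71% of replicates when everyone smoked, and in 40% when half smoked none. The slope of 0.3 is an assumption.

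**Step 2: session count.** A mean over puffs is undefined when there are no puffs. Zero cigarettes (equivalently, every offer resisted) therefore means no topography value. The remaining values come from the same 60 minutes, and the same cigarettes, that make up the count.

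**Step 3: sample size.** The SAP's Power Analysis gives N = 75 at the deprivation assessment. The zero-smoker share q is an assumption. The smallest correlation detectable with 80% power (two-sided 5%, Fisher z) is tanh[(1.960 + 0.842)/√(n − 3)].

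| q | n with topography | Smallest detectable r |
|---|---|---|
| 0% | 75 | .32 |
| 20% | 75 × .8 = 60 | .36 |
| 40% | 75 × .6 = 45 | .41 |

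**Step 4: effect of selection on the correlation.** Assume that topography and the propensity to smoke in the session each load .6 on a common trait, so ρ = .6 × .6 = .36, that they are bivariate normal, and that the lowest fraction q on propensity smokes nothing. With c = Φ⁻¹(q) and λ = φ(c)/(1 − q), the variance of propensity among smokers is v = 1 + cλ − λ², and the smokers-only correlation is ρ√v/√(1 − ρ² + ρ²v).

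- q = 20%: c = −.842, λ = .350, v = .583. The result is .36 × .764/√(.870 + .076) = .283, a loss of about 21%.
- q = 40%: c = −.253, λ = .644, v = .422. The result is .36 × .650/√(.870 + .055) = .243, a loss of about 32%.

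A separate simulation on different assumptions points the same way: a full-sample correlation of .28 became .24, .20 and .17 among smokers when 10%, 30% and 50% smoked none.

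**Step 5: Aim 3.** The SAP defines the Aim 3 predictors as the risk factors, and topography is not one of them. If topography were added in an exploratory version of that model, participants who smoke none would drop out of that version. The planned fit keeps them.

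**The case against.** The strongest reply is that the analysis is exploratory, that Aim 2 is described in terms of bivariate association, and that predictor is ordinary regression vocabulary with no causal claim attached. This limits the severity. It does not settle the point, because the sentence as written places topography on the predictor side of the Aim 2 and Aim 3 models, and an exploratory label changes neither the time order nor who is missing.

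A second reply is that the SAP chose mixed models because they retain participants with missing data. Likelihood methods do so for missing outcomes. They do not by themselves retain a participant whose predictor is undefined, and the SAP supplies no rule for that case.

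A third reply is the SAP's opening note that limited sample size prevented valid execution of the full plan. The note does not say which analyses were dropped, so it does not withdraw this one.

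Three stronger readings might be inferred, and the documents do not support them:
- *That the analysis selects on both outcomes.* A participant who holds out for all 50 minutes still enters the session and may smoke, so latency is not directly truncated. Indirect selection is possible if those who delay longest are also likelier to smoke nothing, but the documents give no figure for this.
- *That the main Aim 3 estimates lose the complete resisters.* Step 5 shows that they do not.
- *That the selection manufactures an association.* In the illustrations for the count it weakens one.

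It is also fair to object that analysing topography as an outcome among smokers uses the same restricted sample. That stands, and the fix must say so.

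**Conclusion.** The point holds as a cheap improvement of minor to moderate severity. There are two separate faults: reversed time order for latency, and a predictor missing because of the outcome for the session count. Both follow from the documents' own description of the procedure and depend on no assumed number.

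The size is illustrative only. It rests on an assumed 20% to 40% smoking nothing (N of 60 or 45) and an assumed full-sample correlation of .36 under normality (about .28 or .24 among smokers). The conclusion is the same whether the second outcome is cigarettes smoked or offers resisted, apart from the sign of the association, but the two names should be reconciled.

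**What to change.** Replace item 3 of the SAP's Exploratory Analyses with text to this effect:

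> Smoking topography will be analysed as an exploratory outcome among participants who smoke in the self-administration session, with the risk variables as predictors. Results are conditional on smoking. The number and proportion who smoked will be reported by arm. Any comparison of topography between arms is descriptive, because smoking in the session occurs after randomisation. Associations of topography with latency or with the session count will be reported only as concurrent correlates among smokers. Topography will not enter the Aim 2 or Aim 3 models.

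This matches the role that the protocol's Design Overview gives topography. It also puts the time order right, since the risk variables are assessed before the lapse paradigm starts. In the same edit, give the second outcome one name in both documents.

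The cost is a short change to SAP text and the alignment of one outcome name, with no new data. The result that topography predicts lapse is given up, but it could not have been interpreted as prediction.
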